## Glossary of terms

Assessment	A procedure used to generate data required by the study
Control drug	Drugs(s) used as a comparator to reduce assessment bias, preserve blinding of investigational drug, assess internal study validity, and/or evaluate comparative effects of the investigational drug
Enrollment	Point/time of patient entry into the study; the point at which informed consent must be obtained (i.e. prior to starting any of the procedures described in the protocol)
Epoch	The planned stage of the subjects' participation in the study. Each epoch serves a purpose in the study as a whole. Typical epochs are: determination of subject eligibility, wash-out of previous treatments, exposure of subject to treatment or to follow-up on subjects after treatment has ended.
Investigational drug	The drug whose properties are being tested in the study; this definition is consistent with US CFR 21 Section 312.3 and is synonymous with "investigational new drug" or "investigational medicinal product."
Investigational treatment	All investigational drug(s) whose properties are being tested in the study as well as their associated treatment controls. This includes any placebos, any active controls, as well as approved drugs used outside of their indication/approved dosage or tested in a fixed combination. Investigational treatment generally does not include other treatments administered as concomitant background therapy required or allowed by the protocol when used within approved indication/dosage
Medication number	A unique identifier on the label of each investigational/study drug package in studies that dispense medication using an IRT system
Subject Number	A number assigned to each patient who enrolls into the study
Part	A subdivision of a single protocol into major design components. These parts often are independent of each other and have different populations or objectives. For example, a single dose design, a multiple dose design that are combined into one protocol, or the same design with different patient populations in each part.
Period	A subdivision of a cross-over study
Premature patient withdrawal	Point/time when the patient exits from the study prior to the planned completion of all investigational/study treatment administration and all assessments (including follow-up)
Randomization number	A unique identifier assigned to each randomized patient, corresponding to a specific treatment arm assignment

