Secondary Objectives	
Secondary objective of this study is:
 
-To test the predictive value of cytokine/chemokine changes measured in the 3rd and 6th months on the PASAT, SDMT, 9-Hole peg test, timed 25-foot walk, EDSS and relapse rate observed after 6 months of treatment.

Study design	This study is a multi-center, open label study.
Population	80 relapsing remitting MS (RRMS) patients will be recruited according to the McDonald's criteria and 60 healthy controls will be recruited as the control group. All subjects will sign an informed consent that will be approved by the local Ethics Committee and the applicable health authorities prior to venipuncture. Basal EDSS, relapses during the last 2 years, paced auditory serial addition task (PASAT), 9-Hole peg test, timed 25-foot walk and single digit modalities test (SDMT) scores will be recorded before study entry. Serum and blood samples will be collected from each participant after evaluation for inclusion and exclusion criteria. Additional serum and blood samples at 2 different time points will be collected from MS patients at months 3 ( $\pm 1$ week) and 6 ( $\pm 2$ weeks) after starting fingolimod 0.5 mg/day po. treatment.

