## **4 Population**

The study will include only 80 relapsing remitting MS patients and 60 healthy controls without any known autoimmune disease. RRMS patients will be followed for 6 months.

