### **4.2 Exclusion criteria**

Patients fulfilling **any** of the following criteria are not eligible for inclusion in this study. No additional exclusions may be applied by the investigator, in order to ensure that the study population will be representative of all eligible patients.

1. Patients with secondary progressive MS.
2. Patients with known contraindications for fingolimod treatment.
3. Other coexistent autoimmune diseases including Hashimoto thyroiditis, systemic lupus erythematosus, rheumatoid arthritis, psoriasis etc.
4. Patients with any of the following cardiovascular conditions:
  - Resting heart rate < 45 bpm/min
  - Cardiac failure at any time during the first study visit (Class III as per NYHA classification) or significant heart disease as judged by the physician
  - Myocardial infarction during the last 6 months
  - History of Mobitz Type II grade 2 AV block
  - Past or current grade 3 AV block
  - Confirmed history of sick sinus syndrome or sino-atrial heart block
  - arrhythmia requiring current treatment with Class Ia drugs (ajmaline, disopyramide, procainamide, quinidine)
  - hypertension uncontrolled with medication
5. History of malignancy of any organ system other than localized basal cell carcinoma of the skin
6. Pregnant or nursing (lactating) women
7. Negative for varicella-zoster virus IgG antibodies at screening
8. History of previous fingolimod therapy

9. Presence of any clinically active infections

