### **5.4 Treating the patient**

#### **5.4.1 Patient numbering**

Each patient is uniquely identified by a Subject Number which is composed by the site number assigned by Novartis and a sequential number assigned by the investigator. Once assigned to a patient, the Subject Number will not be reused.

Upon signing the informed consent form, the patient is assigned the next sequential number as given by the investigator using the next blank CRF book.

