## **9.8 Sample size calculation**

Due to the lack of previous studies using all of the cytokines and chemokines and multitudinous analyses, it is difficult to estimate a precise sample size for our study. Despite this, our previous publications indicate that the basal IL-17 concentration is normally distributed with a mean of 32 pg/ml ( $\pm$ stdev of 15 pg/ml) in RRMS patients. If the true difference in the mean concentration of matched pairs is 7 pg/ml, we will need to study 50 pairs of subjects to be able to reject the null hypothesis with a power of 90%. The Type I error probability associated with this test of this null hypothesis is 0,05.

With assumption of drop out rate of 20% minimum 60 RRMS patients and 60 healthy control subjects should enroll to the study. Due to expected high rate of screen failure patients, we decided to screen 80 RRMS patients in order to reach 60 eligible RRMS subjects for the study.

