5 ANALYZED POPULATIONS

The study will include only 80 relapsing remitting MS patients and 60 healthy controls without any known autoimmune disease. RRMS patients will be followed for 6 months.

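### The planned RRMS sample size is inconsistent (80 screened to reach 60 eligible, or 80 included), and 60 enrolled does not cover the stated 20% dropout

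*Protocol*

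**What the plan says.** Protocol 9.8 and SAP 5.1 carry the same derivation. They start from 50 matched pairs for 90% power on IL-17 and then allow for dropout: "With assumption of drop out rate of 20% minimum 60 RRMS patients and 60 healthy control subjects should enroll to the study". They finish with screening: "we decided to screen 80 RRMS patients in order to reach 60 eligible RRMS subjects for the study". Here 80 is the intake and 60 is the eligible yield.

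Protocol 4 gives 80 a different role. Its text reads: "include only 80 relapsing remitting MS patients and 60 healthy controls without any known autoimmune disease. RRMS patients will be followed for 6 months". SAP 5, headed Analyzed Populations, repeats it: "The study will include only 80 relapsing remitting MS patients and 60 healthy controls". The SAP's sample size section, with the other account, follows directly.

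The Protocol synopsis has a third verb: "80 relapsing remitting MS (RRMS) patients will be recruited". Protocol 3.1 and SAP 4 use the same wording.

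Protocol 5.4.9 says that prematurely withdrawn patients are replaced one for one by new patients.

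**The concern.** The number of patients to be included is a basic design figure, and the two documents give it in two ways. If 80 are screened and some fail, fewer than 80 are included. If 80 are included, more than 80 must be screened. No section reconciles the two. Recruitment targets, drug supply and any later report of planned against actual enrolment all need one number.

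A second, smaller matter sits in the same paragraph. The step from 50 to 60 is presented as an allowance for 20% dropout, but 60 enrolled does not leave 50 after a 20% loss.

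**Working it through.** **Inputs** (Protocol 9.8, SAP 5.1): difference 7 pg/ml; SD 15 pg/ml; type I error 0.05; power 90%; 50 pairs; dropout 20%; at least 60 enrolled; 80 screened; 60 eligible. Sidedness is not stated. I assume a two-sided test and use 15 as the SD of the paired difference, because that combination reproduces the plan's figure.

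**1. The plan's 50 pairs.** Normal approximation: ((z0.975 + z0.90) × 15/7)² = ((1.960 + 1.282) × 2.143)² = 48.2, so 49 pairs. The noncentral t gives 51 pairs, and power at 50 pairs is 0.899. The stated 50 reproduces closely enough.

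**2. The plan's 60 enrolled.** 50 × 1.2 = 60. This is the multiplication the plan appears to have used.

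**3. The plan's 80 screened.** 60/80 = 0.75 eligible, which is 25% screen failure. Nothing in this step is wrong.

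**4. Can 80 also be the number included?**
- Protocol 4.2 says that patients meeting any "of the following criteria are not eligible for inclusion in this study". In the protocol's own usage, then, included patients are those who passed eligibility.
- Protocol 6.1 says that ineligible patients give no serum. They cannot contribute to a population analysed for serum cytokines, and SAP 5 is headed Analyzed Populations.
- The sentence in Protocol 4 and SAP 5 sets 80 beside 60 controls. In 9.8, 60 is the number of controls to enrol. If 80 meant screened, one sentence would count screened patients against enrolled controls.

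On this reading the number included is 60 under 9.8 and SAP 5.1, and 80 under Protocol 4 and SAP 5: 80 − 60 = 20 patients. To include 80 at the implied 75% eligibility, 80/0.75 = 106.7, so about 107 would have to be screened. The documents do not give that figure.

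**5. Does 60 cover 20% dropout?**
- Completers: 60 × (1 − 0.20) = 48, which is 2 below the stated 50.
- Enrolment needed for 50 completers: 50/(1 − 0.20) = 62.5, so 63.
- Dropout that 60 tolerates: 1 − 50/60 = 0.167, or 16.7%.
- For scale, on the plan's paired calculation 48 pairs give power 0.886, against 0.899 at 50.

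**6. Where dropout applies.** Controls are sampled once (Table 6-2), and the patients' baseline sample is taken at Visit 1 (Table 6-1). Follow-up dropout therefore leaves the Day 0 comparison untouched. It bears on the comparisons in SAP 6.5.1 and 6.5.2 that use Visit 2 or Visit 3.

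**The case against.** The best defence is that 80 is a count of consented patients throughout. The Glossary defines enrollment as "Point/time of patient entry into the study; the point at which informed consent must be obtained". Protocol 5.4.1 adds: "Upon signing the informed consent form, the patient is assigned the next sequential number". Protocol 6.1 has no separate screening visit; eligibility is judged at Visit 1. On that usage 80 patients consent and about 60 prove eligible. It can also be said that 60 is only a minimum, so 80 might be a ceiling.

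Part of this stands. *Recruited*, in the synopsis, Protocol 3.1 and SAP 4, can mean consented or screened, so those sections are ambiguous and do not contradict 9.8. The defence is weaker for the word *include* in Protocol 4 and SAP 5, for the reasons in step 4 of the working. The Glossary adds a difficulty of its own: 9.8 applies *enroll* to the 60, while the Glossary would apply it to everyone who consents. The floor-and-ceiling reading does not fit the last sentence of 9.8, which aims at 60 eligible out of 80 screened.

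On dropout, the replacement rule in Protocol 5.4.9 is a fair answer for the patients. What is missing is any link to it in the sample size sections.

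**Conclusion.** The inconsistency holds. The planned number of RRMS patients included is 60 or 80, and the documents do not settle which. The dropout arithmetic is a separate, smaller error: 60 enrolled yields 48 at 20% dropout without replacement, against 50 stated. Both should be corrected. They affect the clarity of the planned numbers; no test changes, and the 50-pair calculation reproduces on the assumptions given above.

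Three stronger readings are tempting, and the documents do not support them.
- A reader might infer that 80 patients are to be followed for six months. The follow-up sentence in Protocol 4 and SAP 5 is a separate sentence and carries no number.
- A reader might add replacements to the 60 and infer a third planned total (60 × 0.2 = 12; 60 + 12 = 72). No such figure is stated, and it depends on assuming a single round of replacement.
- A reader might infer that the analysis sets are in conflict. Protocol 9.1 and SAP 6 take all MS patients and the control group and give no count, so that rule neither resolves the matter nor is changed by it.

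**What to change.** Protocol 9.8, with its copy in SAP 5.1, is the only place where the numbers are derived, so the simplest course is to bring the rest into line with it:

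- In Protocol 4 and SAP 5, replace the statement that 80 are included with 80 screened and 60 enrolled.
- In the synopsis, Protocol 3.1 and SAP 4, replace *recruited* with the matching term. Say whether *enrolled* counts consented patients, as in the Glossary, or eligible ones, as in 9.8.
- In Protocol 9.8 and SAP 5.1, keep 20% as the dropout assumption. Then state either that 60 enrolled gives 48 completers at that rate (it tolerates 16.7%), or that one-for-one replacement under 5.4.9 maintains the 50. Note that follow-up dropout does not touch the controls or the Day 0 comparison.

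This costs wording only and adds no patients. The downside is that, if replacement is not invoked, the stated dropout tolerance looks slightly less favourable.

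If the sponsor means 80 treated, the last sentence of 9.8 and SAP 5.1 must be rewritten and the larger screening number stated: about 107 at 75% eligibility. That is more than a wording change, with 107 − 80 = 27 more patients screened and 80 − 60 = 20 more treated than 9.8 plans.

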## **9.9      Interim analyses**

Not Applicable

## 10 Ethical considerations

### 10.1 Regulatory and ethical compliance

This clinical study was designed and shall be implemented and reported in accordance with the ICH Harmonized Tripartite Guidelines for Good Clinical Practice, with applicable local regulations (including European Directive 2001/20/EC, US Code of Federal Regulations Title 21, and Japanese Ministry of Health, Labor, and Welfare), and with the ethical principles laid down in the Declaration of Helsinki.

### 10.2 Informed consent procedures

Eligible patients may only be included in the study after providing written (witnessed, where required by law or regulation), IRB/IEC-approved informed consent, or, if incapable of doing so, after such consent has been provided by a legally acceptable representative of the patient. In cases where the patient's representative gives consent, the patient should be informed about the study to the extent possible given his/her understanding. If the patient is capable of doing so, he/she should indicate assent by personally signing and dating the written informed consent document or a separate assent form. Informed consent must be obtained before conducting any study-specific procedures (i.e. all of the procedures described in the protocol). The process of obtaining informed consent should be documented in the patient source documents.

Novartis will provide to investigators in a separate document a proposed informed consent form that complies with the ICH GCP guideline and regulatory requirements and is considered appropriate for this study. Any changes to the proposed consent form suggested by the investigator must be agreed to by Novartis before submission to the IRB/IEC, and a copy of the approved version must be provided to the Novartis monitor after IRB/IEC approval.

### 10.3 Responsibilities of the investigator and IRB/IEC

The protocol and the proposed informed consent form must be reviewed and approved by a properly constituted Institutional Review Board/Independent Ethics Committee/Research Ethics Board (IRB/IEC) before study start. A signed and dated statement that the protocol and informed consent have been approved by the IRB/IEC must be given to Novartis before study initiation. Prior to study start, the investigator is required to sign a protocol signature page confirming his/her agreement to conduct the study in accordance with these documents and all of the instructions and procedures found in this protocol and to give access to all relevant data and records to Novartis monitors, auditors, Novartis Clinical Quality Assurance representatives, designated agents of Novartis, IRBs/IECs, and regulatory authorities as required. If an inspection of the clinical site is requested by a regulatory authority, the investigator must inform Novartis immediately that this request has been made.

### 10.4 Publication of study protocol and results

Novartis assures that the key design elements of this protocol will be posted in a publicly accessible database such as clinicaltrials.gov. In addition, upon study completion and

finalization of the study report the results of this trial will be either submitted for publication and/or posted in a publicly accessible database of clinical trial results.

## 11 Protocol adherence

Investigators ascertain they will apply due diligence to avoid protocol deviations. Under no circumstances should the investigator contact Novartis or its agents, if any, monitoring the trial to request approval of a protocol deviation, as requests to approve deviations will not be granted.

This protocol defines the study objectives, the study procedures and the data to be collected on study participants. Under no circumstances should an investigator collect additional data or conduct any additional procedures for any research related purpose involving any investigational drugs.

If the investigator feels a protocol deviation would improve the conduct of the study this must be considered a protocol amendment, and unless such an amendment is agreed upon by Novartis and approved by the IRB/IEC it cannot be implemented. All significant protocol deviations will be recorded and reported in the CSR.

### 11.1 Protocol Amendments

Any change or addition to the protocol can only be made in a written protocol amendment that must be approved by Novartis, Health Authorities where required, and the IRB/IEC. Only amendments that are required for patient safety may be implemented prior to IRB/IEC approval. Notwithstanding the need for approval of formal protocol amendments, the investigator is expected to take any immediate action required for the safety of any patient included in this study, even if this action represents a deviation from the protocol. In such cases, Novartis should be notified of this action and the IRB/IEC at the study site should be informed within 10 working days or less, if required by local regulations.

### 13 Appendix 1: 2005 Revisions to the McDonald diagnosis criteria for MS Guidelines from International Panel on the diagnosis of MS

(McDonald 2001, Polman 2005,)

Clinical Presentation	Additional Data Needed for MS Diagnosis
Two or more attacks; objective clinical evidence of 2 or more lesions	None a
Two or more attacks; objective clinical evidence of 1 lesion	Dissemination in space , demonstrated by: MRI b or Two or more MRI-detected lesions consistent with MS plus positive CSF c or Await further clinical attack implicating a different site
One attack; objective clinical evidence of 2 or more lesions	Dissemination in time , demonstrated by: MRI d or Second clinical attack
One attack; objective clinical evidence of 1 lesion (monosymptomatic presentation; clinically isolated syndrome)	Dissemination in space , demonstrated by: MRI b or Two or more MRI-detected lesions consistent with MS plus positive CSF c and Dissemination in time , demonstrated by: MRI d or Second clinical attack

If the criteria indicated are fulfilled, the diagnosis is multiple sclerosis (MS)

aNot additional tests are required; however, if tests [magnetic resonance imaging (MRI), cerebral spinal fluid (CSF)] are undertaken and are negative, extreme caution should be taken before making a diagnosis of MS. Alternative diagnoses must be considered. There must be no better explanation for the clinical picture.

bMRI demonstration of space dissemination must fulfill the criteria listed below.

cPositive CSF determined by oligoclonal bands detected by established methods (preferably isoelectric focusing) different from any such bands in serum or by a raised IgG index.

dMRI demonstration of time dissemination must fulfill the criteria listed below.

## **14 Appendix 2: Instructions for the Paced Auditory Serial Addition Test (PASAT)**

The PASAT is a measure of cognitive function that specifically assesses auditory information processing speed and flexibility, as well as calculation ability. The PASAT is the last measure administered at each visit. It is presented on audio CD to control the rate of stimulus presentation. Single digits are presented every 3 seconds and the patient must add each new digit to the one immediately prior to it. The test result is the number of correct sums given (out of 60 possible). To minimize familiarity with stimulus items in clinical trials and other serial studies, two alternate forms have been developed; the order of these should be counterbalanced across testing sessions.

### **MATERIALS NEEDED**

CD player, audio CD with PASAT stimuli, clipboard, PASAT Record Forms

## **15 Appendix 3: EDSS Assessment Criteria**

### **EXPANDED DISABILITY STATUS SCALE**

**0**= normal neurological exam (all FS grade 0)

**1.0** = no disability, minimal signs in one FS (one FS grade 1)

**1.5** = no disability, minimal signs in more than one FS (more than one FS grade 1)

**2.0** = minimal disability in one FS (one FS grade 2, others 1 or 0)

**2.5** = minimal disability in two FS (two FS grade 2, others 1 or 0)

**3.0** = moderate disability in one FS (one FS grade 3, others 1 or 0) though fully ambulatory; or mild disability in three or four FS (three/four FS grade 2, others 1 or 0) though fully ambulatory

**3.5** = fully ambulatory but with moderate disability in one FS (one FS grade 3) and mild disability in one or two FS (one/two FS grade 2) and others 0 or 1; or fully ambulatory with two FS grade 3 (others 0 or 1); or fully ambulatory with five FS grade 2 (others 0 or 1)

**4.0** = ambulatory without aid or rest for 3500 meters; up and about some 12 hours a day despite relatively severe disability consisting of one FS grade 4 (others 0 or 1) or combinations of lesser grades exceeding limits of previous steps

**4.5** = ambulatory without aid or rest for 3300 meters; up and about much of the day, characterised by relatively severe disability usually consisting of one FS grade 4 and combination of lesser grades exceeding limits of previous steps

**5.0** = ambulatory without aid or rest for 3200 meters (usual FS equivalents include at least one FS grade 5, or combinations of lesser grades usually exceeding specifications for step 4.5)

**5.5** = ambulatory without aid or rest 3100 meters

**6.0** = unilateral assistance (cane or crutch) required to walk at least 100 meters with or without resting

**6.5** = constant bilateral assistance (canes or crutches) required to walk at least 20 meters without resting

**7.0** = unable to walk 5 meters even with aid, essentially restricted to wheelchair; wheels self and transfers alone; up and about in wheelchair some 12 hours a day

**7.5** = unable to take more than a few steps; restricted to wheelchair; may need some normal neurological exam (all FS grade 0) no disability, minimal signs in one FS (one FS grade 1) no disability, minimal signs in more than one FS (more than one FS grade 1) minimal disability in one FS (one FS grade 2, others 0 or 1) minimal disability in two FS (two FS grade 2, others 0 or 1) moderate disability in one FS (one FS grade 3, others 0 or 1) though fully help in transferring and in wheeling self

**8.0** = essentially restricted to bed or chair or perambulated in wheelchair, but out of bed most of day; retains many self-care functions; generally has effective use of arms

**8.5** = essentially restricted to bed much of the day; has some effective use of arm(s); retains some self-care functions

**9.0** = helpless bed patient; can communicate and eat

**9.5** = totally helpless bed patient; unable to communicate effectively or eat/swallow

**10.0** = death due to MS
